Visit c	V1	V2	V3	V4	V5	V6**	V7**	V8	Telephone Contact d	V9	V10**	V11	ET Visit e	Termination Visit f	Unscheduled Visit
Week	0	2	6	14	22	30	38	46		62	78	94			NA
Endocrinology p	X*												X	X	
Pregnancy test q	X	X	X	X	X			X		X		X	X	X	
Call IRT	X	X	X	X	X			X		X		X	X	X	X
C-SSRS r	X	X	X	X	X			X		X		X	X	X	X
Dispense subject diary	X	X	X	X	X			X		X		X	X	X	
Subject diary return/review		X	X	X	X			X		X		X	X	X	X
Dispense LCM	X	X	X	X	X			X		X		X	X	X	
LCM review/return		X	X	X	X			X		X		X	X	X	
Withdrawal criteria	X*	X	X	X	X			X	X	X		X	X	X	X
AE reporting	X*	X	X	X	X			X	X	X		X	X	X	X
EQ-5D-3L	X				X			X		X		X	X	X	
QOLIE-31-P/PedsQL s	X				X			X		X		X	X	X	
Achenbach CBCL t	X				X			X		X		X	X	X	
BRIEF-P/BRIEF u	X				X			X		X		X	X	X	
Healthcare resource use	X*	X	X	X	X			X		X		X	X	X	
Work/school days lost due to epilepsy	X*	X	X	X	X			X		X		X	X	X	

**Table 5–1: Schedule of study assessments for Years 1 and 2 for EP0012 (Treatment Period, ET Visit, Termination Visit, and Unscheduled Visit)**

	Treatment Period a													Unscheduled b	
Duration	Open-label: at least 2 years													NA	
Year of study	Year 1								Year 2						
Visit c	V1	V2	V3	V4	V5	V6**	V7**	V8	Telephone Contact d	V9	V10**	V11	ET Visit e	Termination Visit f	Unscheduled Visit
Week	0	2	6	14	22	30	38	46		62	78	94			NA
Days with help from a caregiver due to epilepsy	X*	X	X	X	X			X		X		X	X	X	

AE=adverse event; AED=antiepileptic drug; BP=blood pressure; BRIEF=Behavior Rating Inventory of Executive Function; BRIEF-P=Behavior Rating Inventory of Executive Function-Preschool Version; CBCL=Child Behavior Checklist; C-SSRS=Columbia-Suicide Severity Rating Scale; ECG=electrocardiogram; EQ-5D-3L=3-level EuroQol-5 Dimension Quality of Life Assessment; ET=early termination; exam=examination; ID=identification; IRT=interactive response technology; LCM=lacosamide; NA=not applicable; PedsQL=Pediatric Quality of Life Inventory; QOLIE-31-P=Patient Weighted Quality of Life in Epilepsy Inventory-Form 31; V=Visit

Note: For subjects who have completed SP0982, assessments marked (\*) should have already been completed during the last visit of the previous protocol and do not need to be repeated at Visit 1; for eligible Baseline failures from SP0982, a full Visit 1 is required including all scheduled tasks and procedures.

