- j The brief neurological examination will include selected assessment of general neurological status, reflexes, muscle strength, and coordination/cerebellar function.
- k The ECG recordings should be performed at the same time of day (when possible) and prior to blood sample collection and vital sign assessments. Care should be taken to assure proper lead placement and quality ECG recordings. If possible, subjects should rest in a supine position at least 5 minutes prior to each recording and should be motionless during the recording. In pediatric subjects (<18 years of age) a 12-lead ECG (2 interpretable recordings) approximately 20 to 30 minutes apart must be performed.
- l Blood pressure measurements should be taken with the proper placement and proper sized cuff to obtain accurate measurements.
- m Height will be recorded at Visits 1 and 9, and at the ET and Termination Visit.
- n The Tanner Stage will be performed only for subjects who are pubescent at Visit 1 or who enter puberty during the course of the study.
- o Urinalysis will be required for all subjects.
- p If the patient was treated in SP0982, endocrinology should be done if age was <18 years at SP0982 Visit 1. If the patient was a Baseline failure in SP0982, endocrinology should be done if age is <18 years at EP0012 Visit 1.
- q Pregnancy tests will be performed for female subjects of childbearing potential only. Serum pregnancy tests will be conducted at the following visits: Visit 1 (W0), ET, and Termination Visit. All other pregnancy tests will be urine dipstick. Baseline failures from SP0982 may have an additional urine pregnancy test at V1 of EP0012, at the investigator's discretion.
- r The C-SSRS will be completed for all subjects  $\geq 6$  years of age (see [Section 10.4.3](#)).

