**Table 5-4: Schedule of study assessments (Taper Period and Safety Follow-Up Period)**

Assessment	Taper Period a (up to 4 weeks)	Safety Follow-Up Period b	
	End of Taper Visit (maximum 3 days after the last dose) c	Safety Follow-Up Visit	Safety Follow-Up TC
		2 weeks (±2 days) after last dose of study drug	30 days (-1/+3 days) after last dose of study drug
Concomitant medications and AED(s)	X	X	X
Physical exam (complete)	X	X	
Neurological exam (brief)	X	X	
12-lead ECG d	X	X e	
Vital signs (BP and pulse) including orthostatic assessments	X	X	
Body weight	X	X	
Laboratory tests:			
Chemistry/hematology	X	X e	
Endocrinology		X e	
Urine pregnancy test f	X	X	
Contact IRT	X		
Subject diary return/review g	X		
LCM review/return	X		
Withdrawal criteria	X		
AE reporting	X	X	X
C-SSRS h	X	X	
Healthcare resource use i	X	X	
Work/school days lost due to epilepsy i	X	X	
Days with help from a caregiver due to epilepsy i	X	X	

AE=adverse event; AED=antiepileptic drug; BP=blood pressure; C-SSRS=Columbia-Suicide Severity Rating Scale; ECG=electrocardiogram; IRT=interactive response technology; LCM=lacosamide; TC=telephone contact

Note: The schedule of study assessments for the Taper Period and Safety Follow-Up Visit includes some of the subjects who tapered in SP0982 after the 125th event who consented to enter EP0012 for the Safety Follow-Up only.

a Subjects who will not continue on LCM must complete an End of Taper Visit and a Safety Follow-Up Period; see Table 5-4. For subjects who continue on commercial LCM, the (Early) Termination Visit is the last visit in the study.

- b There will be a 30-day (-1/+3 days) Safety Follow-Up Period for subjects who complete the End of Taper Visit. The Safety Follow-Up Period consists of a clinic visit 2 weeks after the End of Taper Visit followed 2 weeks later by a TC Visit.
- c An End of Taper Visit will be scheduled at the end of the Taper Period (up to 4 weeks) depending on dose level achieved; see [Table 7-2](#). Of note, for subjects who enter the Taper Period at  $\leq 2$ mg/kg/day (oral solution) or 100mg/day (tablets), the End of Taper Visit will take place at the ET or Termination Visit.

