- d The ECG recordings should be performed at the same time of day (when possible) and prior to blood sample collection and vital sign assessments. Care should be taken to assure proper lead placement and quality ECG recordings. If possible, subjects should rest in a supine position at least 5 minutes prior to each recording and should be motionless during the recording. In pediatric subjects (<18 years of age) a 12-lead ECG (2 interpretable recordings) approximately 20 to 30 minutes apart must be performed.
- e The assessment will only be required for subjects with an abnormal value (clinical chemistry, hematology, or endocrinology) or reading (ECG) at the previous clinic visit.
- f Pregnancy tests will be performed for female subjects of childbearing potential only. A urine pregnancy test will be performed.
- g The last subject diary will be returned at the End of Taper Visit.
- h The C-SSRS will be completed for all subjects  $\geq 6$  years of age (see [Section 10.4.3](#)).
- i Healthcare resource use, work/schools days lost due to epilepsy, and days with help from a caregiver due to epilepsy will be assessed only for patients completing the study after  $\leq 2$  years. These assessments are not applicable for patients tapering down or performing the SFU-visits during Years 3, 4 or 5).

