## **8.2 Early Termination Visit**

Subjects withdrawing from the study will complete the ET Visit, and LCM will be tapered over a period of up to 4 weeks if not continuing with commercially available LCM (see taper schedule, [Table 7-2](#)).

The following tasks and procedures are to be performed at this visit:

- Concomitant medications and AEDs

- Physical examination (complete), excluding subjects  $\geq 18$  years after the first 2 years
- Neurological examination (brief), excluding subjects  $\geq 18$  years after the first 2 years
- ECG (12-lead) assessment, excluding subjects  $\geq 18$  years after the first 2 years
- Vital signs (pulse rate, BP) including orthostatic assessments, excluding subjects  $\geq 18$  years after the first 2 years
- Body weight and height, excluding subjects  $\geq 18$  years after the first 2 years
- Tanner staging (will be performed only for subjects who are pubescent at Visit 1 or who enter puberty during the course of the study), excluding subjects  $\geq 18$  years after the first 2 years
- C-SSRS assessment (for subjects  $\geq 6$  years of age), excluding subjects  $\geq 18$  years after the first 2 years
- Blood and urine samples for clinical laboratory assessments (includes hematology, chemistry, endocrinology for subjects  $< 18$  years of age at Visit 1, urinalysis, and a serum pregnancy test [for women of childbearing potential])
- Contact IRT
- Dispense subject diary
- Subject diary return/review
- Dispense LCM
- LCM review/return
- Assess withdrawal criteria
- AE reporting
- Achenbach CBCL for subjects  $< 18$  years of age
- BRIEF for subjects  $< 18$  years of age

The following assessments are only applicable at the ET Visit for subjects early terminating the study within the first 2 years (see Section 4.2.3):

- EQ-5D-3L (for subjects  $\geq 12$  years of age)
- QOLIE-31-P (for subjects  $\geq 18$  years of age)/PedsQL (for subjects  $< 18$  years of age)
- Healthcare resource use
- Work/school days lost due to epilepsy
- Days with help from a caregiver due to epilepsy

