## 8.4 Taper and Safety Follow-Up Period

### 8.4.1 End of Taper Visit

An End of Taper Visit will occur after the final LCM dose for subjects who taper off LCM. The following tasks and procedures are to be performed at this visit:

- Concomitant medications and AEDs
- Physical examination (complete)
- Neurological examination (brief)
- ECG (12-lead) assessment
- Vital signs (pulse rate, BP) including orthostatic assessments
- Body weight
- C-SSRS assessment (for subjects  $\geq 6$  years of age)
- Blood and urine samples for clinical laboratory assessments (includes hematology, chemistry, and a urine pregnancy test [for women of childbearing potential])
- Contact IRT
- Subject diary return/review
- LCM review/return
- Assess withdrawal criteria
- AE reporting

The following assessments are only applicable at the End of Taper Visit for subjects terminating/early terminating the study during the first 2 years (see Section 4.2.3):

- Healthcare resource use
- Work/school days lost due to epilepsy
- Days with help from a caregiver due to epilepsy

Subjects who were already tapered in SP0982 after the 125th event occurred do not need to undergo the End of Taper Visit assessments in EP0012 as the assessments were performed in SP0982.

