#### **8.4.2 Safety Follow-Up Visit**

Following the End of Taper Visit, the subject will return 2 weeks after the last dose of study drug for a Safety Follow-Up Visit (including subjects tapered in SP0982 after the 125th event occurs who enter EP0012 only for a Safety Follow-Up Visit). During the Safety Follow-Up Visit, the following assessments will be performed:

- Concomitant medications and AEDs
- Physical examination (complete)
- Neurological examination (brief)
- ECG (12-lead) assessment (only required for subjects with an abnormal reading at the previous clinic visit)
- Vital signs (pulse rate, BP) including orthostatic assessments
- Body weight
- C-SSRS assessment (for subjects  $\geq 6$  years of age)
- Blood and urine samples for clinical laboratory assessments (includes hematology, chemistry, endocrinology, [only required for subjects with an abnormal value at the previous clinic visit], and a urine pregnancy test [for women of childbearing potential])
- AE reporting

The following assessments are only applicable at the Safety Follow-Up Visit for subjects terminating/early terminating the study during the first 2 years (see Section 4.2.3):

- Healthcare resource use
- Work/school days lost due to epilepsy
- Days with help from a caregiver due to epilepsy

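### For paediatric-entry subjects who taper, the Safety Follow-Up endocrinology trigger looks back to the End of Taper Visit, where endocrinology is not drawn, so read literally an isolated abnormal thyroid result at ET/Termination does not trigger the retest

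*Protocol*

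**What the plan says.** **Where endocrinology is drawn.** Table 10-2 lists it as TSH, T3 and T4. Tables 5-1 and 5-2 place it at Visit 1, ET and Termination only. The Section 8.2 laboratory panel at ET "includes hematology, chemistry, endocrinology for subjects" under 18 at Visit 1, and Section 8.3 has the same item at Termination. Eligibility is set by a footnote to Tables 5-1 and 5-2: "If the patient was treated in SP0982, endocrinology should be done if age was <18 years at SP0982 Visit 1". For Baseline failures the age at EP0012 Visit 1 counts instead.

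**What happens at End of Taper.** The endocrinology cell for this visit in Table 5-4 is blank. Section 8.4.1 lists the samples as "Blood and urine samples for clinical laboratory assessments (includes hematology, chemistry, and a urine pregnancy test [for women of childbearing potential".

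**What happens at Safety Follow-Up.** Table 5-4 marks endocrinology with footnote e, which limits it to cases "for subjects with an abnormal value (clinical chemistry, hematology, or endocrinology) or reading (ECG) at the previous clinic visit". Section 8.4.2 says the same: "endocrinology, [only required for subjects with an abnormal value at the previous clinic visit". That section also sets the order of visits: Safety Follow-Up comes after End of Taper, timed at 2 weeks from the last dose.

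**The concern.** The condition looks back one clinic visit. For ECG, chemistry and hematology that works, because all three are done at End of Taper. For endocrinology it does not, because the last scheduled draw is one visit further back. The End of Taper Visit can supply no endocrinology result, normal or abnormal, so on the planned sequence the endocrinology part of the condition cannot be met.

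At stake is a safety check in young subjects. The Safety Follow-Up Visit is the only scheduled occasion on which an abnormal end-of-treatment thyroid value could be repeated off drug. Naming endocrinology in footnote e, and giving it its own Safety Follow-Up cell, shows that a retest was meant to be available. Two sites could handle the same abnormal value differently and both defend what they did.

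**Working it through.** The protocol gives no figure on this point, so the check is a trace of the schedule followed by a short timing calculation.

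**Visit sequence for an eligible subject with a separate End of Taper Visit**

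| Visit | Endocrinology | Chemistry/hematology | ECG |
|---|---|---|---|
| ET or Termination | drawn (Tables 5-1, 5-2; 8.2, 8.3) | drawn | done |
| End of Taper | not drawn (Table 5-4; 8.4.1) | drawn | done |
| Safety Follow-Up | only if abnormal at the previous clinic visit | same condition | same condition |

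Take a subject with an abnormal TSH at Termination and normal chemistry, hematology and ECG at End of Taper. The previous clinic visit holds no abnormal value and no endocrinology value, so the condition is not met. The word *isolated* matters. Footnote e groups the laboratory panels together, so an abnormal chemistry or hematology value at End of Taper might be read as triggering endocrinology too.

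**Time from the ET/Termination draw to Safety Follow-Up**

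Inputs:
- Table 7-2, with taper starting at ET/Termination. Taper weeks by row are 4, 4, 3, 2, 1 for the five oral-solution rows (from 11 or 12 mg/kg/day down to 4 mg/kg/day), and 4, 4, 4, 4, 3, 2, 1 for the seven tablet rows (800 down to 200 mg/day). All 12 rows are used because the eligibility footnote can include a subject who was under 18 at SP0982 Visit 1 but an adult by EP0012 Visit 1. Shortest 1 week, longest 4 weeks.
- Table 5-4: Safety Follow-Up is 2 weeks (±2 days) after the last dose.
- Section 5.1.1 and Table 5-4: End of Taper is at most 3 days after the last dose. Section 5.1.1, Section 7.2.1 and Table 5-4 footnote b count the 2 weeks from that visit instead.

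Nominal interval: 1 + 2 = 3 weeks to 4 + 2 = 6 weeks.

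Counted from the last dose: (3 × 7) − 2 = 19 days to (6 × 7) + 2 = 44 days.

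Counted from End of Taper: up to 3 days are added, so the upper end becomes 44 + 3 = 47 days. This assumes that the same ±2-day window applies to that anchor.

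**The case against.** **A workable reading exists.** The text says previous, not immediately preceding. Since ET/Termination is the only end-of-treatment draw, a site could take the phrase to mean the last visit at which that test was done. This is the only reading that gives the endocrinology trigger any effect on the taper route, and some sites will adopt it. It stands as a mitigation, but the text does not say it, and the more natural reading is the next visit back.

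**Other routes catch a meaningful abnormality.** The condition sets a minimum and forbids nothing. An abnormal laboratory finding can be recorded as an AE (10.1.1.1) and is then followed up (10.1.3), and Section 8.5 allows laboratory tests at an Unscheduled Visit. This stands in part. Each route depends on the investigator's judgement and none schedules a thyroid test. What is lost is the automatic repeat.

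**Endocrinology is a minor item.** It is not named among the primary, secondary or other safety variables in Section 4.1, nor among the AEs of special interest or the withdrawal criteria. That is correct and limits the weight of the point. It is still in Table 10-2, and Section 12.3.1 says the Section 10.3 laboratory measurements will be presented.

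**A wider failure might be inferred, but is not shown.** A reader might conclude that no young subject leaving the study can trigger the retest. The documents do not support that. For taper entry at or below 2 mg/kg/day or 100 mg/day, "the End of Taper Visit will take place at the ET or Termination Visit", so the look-back lands on a visit with endocrinology. An immediate stop for pregnancy (10.1.4) or on liver criteria (6.3, 6.3.1) may also leave no separate End of Taper Visit. Subjects moving to commercial lacosamide have no Safety Follow-Up. Subjects entering EP0012 for Safety Follow-Up only "do not need to undergo the End of Taper Visit assessments in EP0012 as the assessments were performed in SP0982", and Visit 1 endocrinology is among the items that, for subjects who completed SP0982, "should have already been completed during the last visit of the previous protocol and do not need to be repeated at Visit 1". Whether the rule works for Safety Follow-Up-only entrants cannot be judged from this document.

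**Conclusion.** The point holds for subjects who meet the age footnote, have endocrinology drawn at ET or Termination, and taper in EP0012 with a separate End of Taper Visit. This is the ordinary taper route, since the minimum doses in Table 7-1 (4 mg/kg/day or 200 mg/day) lie above the low-dose exception. On that route the trigger, read literally, cannot respond to an isolated abnormal thyroid value. The table and the procedures text agree with each other, so neither corrects the other.

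It should be corrected, but its reach is limited. No primary or secondary variable is affected, and neither the number of subjects nor the rate of abnormal thyroid values is given, so the number of missed retests cannot be estimated. It would go too far to say that the protocol prevents a retest or that a thyroid signal will be missed.

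The interval of about 3 to 6 weeks rests on the recommended taper. Section 7.2.1 allows slower and faster tapers, so it is not a fixed range. The trace also assumes no unscheduled clinic visit between End of Taper and Safety Follow-Up, because such a visit could become the previous clinic visit.

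**What to change.** In Table 5-4 footnote e and in Section 8.4.2, require endocrinology at Safety Follow-Up when the ET or Termination endocrinology result was abnormal. Leave the ECG and chemistry/hematology triggers as they are, because they already point to a visit where those tests are done.

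Naming ET or Termination is better than referring to the most recent endocrinology result from any visit. If the ET draw were missed, that wording could reach back to a Visit 1 value from years earlier, and it would extend the rule to Safety Follow-Up-only entrants, for whom no failure has been shown.

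The cost is one phrase in two places and probably a small number of extra thyroid tests at a visit already scheduled. The document does not allow that number to be calculated.

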### 5.3 Rationale for study design and selection of dose

Clinical experience has shown that up to 30% of patients with PGTCS who are treated with currently available AEDs have inadequate seizure control or poor drug tolerability. Thus, there is a significant unmet medical need for new treatment options in this patient population.

The efficacy, safety, and tolerability of LCM as an adjunctive therapy have been demonstrated in the partial-onset seizure population. The approach for further LCM development is to evaluate the use of adjunctive LCM for the treatment of uncontrolled PGTCS in patients with IGE.

The goal of the Phase 3 LCM PGTCS program is to provide clinical evidence of the efficacy and safety of LCM as an adjunctive therapy for uncontrolled PGTCS in subjects with IGE as the basis for approval of this indication. SP0982 is a double-blind, randomized, placebo-controlled, parallel-group, multicenter study designed to evaluate the efficacy and safety of LCM for uncontrolled PGTCS in subjects  $\geq 4$  years of age with IGE. EP0012 will provide continued availability of LCM to subjects who have completed SP0982 and eligible Baseline failures from SP0982.

For adult subjects ( $\geq 18$  years of age), the LCM 400mg/day maintenance dose was well tolerated and demonstrated efficacy in 3 primary efficacy studies as adjunctive therapy in subjects with partial-onset seizures. In SP0961 (the Phase 2 pilot study) and SP0962 (the open-label extension study) in subjects with uncontrolled PGTCS with IGE, the 400mg/day dose was also well tolerated. Generally, the doses of AEDs used for the treatment of partial-onset seizures are similar to those used to treat generalized seizures. Thus, the 300mg/day to 400mg/day target dose range is considered the optimal maintenance dose for the population with uncontrolled PGTCS with IGE. The maximum dose of LCM 800mg/day is the highest dose that has been used in previous clinical studies. Dose selection in EP0012 is based on the primary study (SP0982). During EP0012, investigators will be allowed to increase or

decrease the dose of LCM to optimize tolerability and seizure reduction for each subject. Lacosamide doses may be increased up to a maximum of LCM 12mg/kg/day (oral solution) for pediatric subjects weighing <50kg. The maximum dose for pediatric subjects (<18 years of age)  $\geq$ 50kg is 600mg/day (tablets) and for adult subjects is 800mg/day (tablets).

## **6 SELECTION AND WITHDRAWAL OF SUBJECTS**

### **6.1 Inclusion criteria**

To be eligible to participate in this study, all of the following criteria must be met:

1. An Institutional Review Board (IRB)/Independent Ethics Committee (IEC) approved written Informed Consent/Assent form for the open-label extension study (EP0012) must be signed and dated by the subject or by the parent(s) or legal representative. The Informed Consent form or a specific Assent form, where required, will be signed and dated by minors.
2. Subject must have completed or be an eligible Baseline failure from the parent study (SP0982), as defined in Section 5.1. Note: Other subjects screened for SP0982 may be considered for roll-over to EP0012 if the investigator considers that the subject could benefit from treatment with open-label LCM and based on prior discussion with and approval from the UCB Study Physician or representative.
3. Subject/legally acceptable representative considered as reliable and capable of adhering to the protocol (eg, able to understand and complete diaries and questionnaires), visit schedule, and medication intake according to the judgment of the investigator.

